**Table 3: Dose Limiting Toxicities**

Toxicity Category	Dose-Limiting Toxicity/CTCAE (version 5.0) Grade
Hematological toxicity	
 
Grade 4 neutropenia lasting more than 5 days
 
Grade 3 febrile neutropenia (ANC <math><1.0 \times 10^9/L</math> fever <math>\geq 38.4^{\circ}\text{C}</math> or <math>\geq 38^{\circ}\text{C}</math> for 1 hour)
 
Grade 3 thrombocytopenia with clinically significant bleeding
 
Grade 4 thrombocytopenia
 
Grade 4 Anemia unexplained by underlying disease
 

Other non-hematological toxicity	
 
Any other non-hematologic toxicity <math>\geq 3</math> except: 
 
Alopecia
 
Grade 3 nausea/vomiting or diarrhea for less than 3 days with adequate antiemetic and other supportive care
 
Grade 3 fatigue for less than one week
 
Grade 3 or higher isolated electrolyte abnormalities that last up to 3 days, are not clinically complicated, and resolve spontaneously, or respond to conventional medical interventions
 
Grade 3 or higher amylase or lipase elevation that is not associated with symptoms or clinical manifestations of pancreatitis
 
Grade 3 tumor lysis syndrome (TLS) that lasts up to 3 days, is not clinically complicated, and resolves spontaneously, or responds to conventional medical interventions.
 
 
 
Any patient meeting Hy's Law Criteria without alternate explanation, concurrent values of: 
 
ALT or AST elevation of <math>>3\times\text{ULN}</math>, and
 
TBL elevation of <math>>2\times\text{ULN}</math>, and
 
Absence of initial findings of cholestasis (ie, absence of elevation of ALP to <math>>2\times\text{ULN}</math>)
 
 
 

AE = adverse event; ALP = alkaline phosphatase; ALT = alanine aminotransferase; AST = aspartate aminotransferase; CTCAE = Common Terminology Criteria for Adverse Events; ECOG = Eastern Cooperative Oncology Group (ECOG); TBL = total bilirubin; ULN = upper limit of normal

*Note:* ALT is also referred to as serum glutamic pyruvic transaminase (SGPT); AST is also referred to as serum glutamic oxaloacetic transaminase (SGOT)

### 7.5.2. Dose Reductions and Interruptions

EZM0414 dose adjustments/reductions and interruptions will be allowed. However, an interruption in the administration of EZM0414, for more than **14 days** must be discussed with the Sponsor's or Designee Medical Monitor before treatment can be resumed.

Toxicity will be managed by concomitant medication (as appropriate), treatment interruption, dose reduction, and treatment discontinuation, or a combination of these. During treatment with study drug, dose interruption and reduction for subjects who experience study drug-related toxicity will be in accordance with the Dose Modifications Instructions in [Table 4](#).

For subjects who require dose interruption due to study drug-related toxicity, the treatment may restart once the toxicity has resolved to Grade  $\leq 1$  or baseline according to the Dose Modifications Instructions in [Table 4](#). If clinically appropriate thereafter re-escalation can be considered in consultation with the Sponsor's Medical Monitor.

Based up on physical exam and respiration rate, follow-up examination should be performed as clinically indicated. For continuation of treatment for cycle 2 and beyond, subjects must meet the following retreatment criteria:

- Platelet count must be  $\geq 50 \times 10^9/L$ , include transfusion dependent subjects
- Absolute neutrophil count (ANC) must be  $\geq 1.0 \times 10^9/L$  if no lymphoma infiltration of bone marrow **OR** ANC must be  $\geq 0.75 \times 10^9/L$  with bone marrow infiltration, and
- Any Grade 3 or higher toxicity must have resolved to Grade 1 or baseline, unless otherwise noted.

The suggested dose reductions for the three lowest dose levels are as follows based on the dose reduction increments included in [Table 4](#):

- Starting dose: 100 mg QD EJM0414
  - 1st dose reduction 75 mg
  - 2nd dose reduction: 50 mg
- Step down dose (if needed): 75 mg QD EJM0414: 1st dose reduction 50 mg and 2nd dose reduction: 25 mg
- Starting dose: 200 mg QD EJM0414
  - 1st dose reduction 150 mg
  - 2nd dose reduction: 100 mg
- Starting dose: 300 mg QD EJM0414
  - 1st dose reduction 200 mg
  - 2nd dose reduction: 100 mg

All final decisions on dose reductions in response to drug-related AEs should be made after discussion with the Sponsor's Medical Monitor.

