**Figure 4: Flowchart for Trial Conduct Using the BOPIN design**

$$* \text{DLT rate} = \frac{\text{Total number of patients who experienced DLT at the current dose}}{\text{Total number of evaluable patients treated at the current dose}}$$

A screening visit will occur within 28 days of signing an informed consent form (ICF). In Cycle 1 (except Day 2 and Day 3), EZM0414 will be administered orally once daily (QD) without food (no food two hours prior and one hour after EZM0414 dose, water is permitted without restrictions) in continuous 28-day cycles. Subjects will continue to receive treatment at the assigned dose level until disease progression, occurrence of unacceptable toxicity, withdrawal of consent, or need for treatment prohibited on this study. No intra-patient dose escalation will be permitted. DLT (as defined in [Table 3](#)) will be assessed during the first treatment cycle. Dose modifications for EZM0414 are discussed in [Table 4](#).

Safety assessments will be performed throughout the study and at each study visit. Vital signs including blood pressure, respiration rate, heart rate, and temperature will be collected according to schedule of assessments ([Table 8](#) and [Table 9](#)).

A single 12-lead ECG will be collected at screening and triplicate ECGs 1-minute apart will be collected at all other time points mentioned in [Table 8](#) and [Table 9](#). Subjects should be rested in a sitting position for 10 min prior to collection of all study ECGs.

Blood samples will be collected from all subjects for PK analyses at time points mentioned in [Table 9](#).

At time points where vital signs, ECG and PK blood samples are required, the following order of collection is recommended (1) vital signs, (2) ECG (3) Blood sample for PK analyses and biomarker analyses.

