**Table 4: Dose Modifications Instructions for Grade 1 – Grade 4 study drug-related Adverse Events\***

Toxicity a	During Therapy	Approximate Study Drug Dose Adjustment b
Excluding fatigue, alopecia, nausea, vomiting, or diarrhea not receiving adequate medical treatment. For management of QTcF prolongation please refer to Section 7.5.3, AST/ALT elevations please refer to Table 5, creatinine elevations please refer to Table 6, and INR elevations please refer to Table 7.		
Grade 1		
All occurrences	Continue study drug	Maintain dose level
Grade 2c		
Toxicity	During therapy	Approximate Study Drug Dose Adjustment b
1st occurrence	Monitor as clinically indicated	Maintain dose level
2nd occurrence	Interrupt study drug until resolved to Grade $\leq 1$ or baseline b	Maintain dose level
3rd occurrence	Discontinue study drug	Restart at one lower dose level
4th occurrence		Not applicable
Grade 3c,d		
Toxicity	During therapy	Approximate Study Drug Dose Adjustment b
1st occurrence	Interrupt study drug until resolved to Grade $\leq 1$ or baseline b	Restart at one lower dose level
2nd occurrence		Restart at second lower dose level
3rd occurrence	Discontinue study drug	Not applicable
Grade 4		
Any occurrence	Discontinue study drug	Not applicable

AST = aspartate aminotransferase; ALT = alanine aminotransferase; INR = international normalized ratio

\* Subjects diagnosed with a Covid-19 positive PCR test will be discontinued from treatment.

a The term occurrences applies to same AE term and not any AE term.b An interruption of any study drug for more than 14 days due to any toxicity must be discussed with the Sponsor's or Designee Medical Monitor before treatment can be resumed.c Excluding Grade 2 and 3 anemia: Subjects are allowed to continue study drug at their current dose level with transfusion per Investigator discretion.d Use of growth factors (G-CSF, GM-CSF) is permitted as per ASCO and ESMO guidelines

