**Table 14: Total Daily Dose and Respective Dose Level**

Dose Level	Total Daily Dose (mg)
-1 (optional)	75
1	100
2	200
3	300
4	400
5	600
6	900

Additional daily dose levels and/or dosing schedules (including BID regimen) may be studied based on clinical and pharmacokinetic data obtained during this study.

Bayesian optimal interval design ([Liu, 2015; Yuan, 2016; Zhou, 2017](#)) will be used for this dose escalation part. Similar numbers of subjects with R/R MM or R/R DLBCL will be enrolled to determine MTD. The target toxicity rate ( $\varrho_T$ ) for the MTD is set at **0.25** for both R/R MM and R/R DLBCL. The maximum number of subjects for determination of MTD is 9. A total of 6 dose levels ( $j = 6$ , ie, starting at 100 mg, then 200 mg, 300 mg, 400 mg, 600 mg, and 900 mg) as well as an optional step-down dose level of 75 mg will be investigated. We will enroll and treat subjects in groups of at least 3, and up to 36 subjects will be enrolled in this dose-escalation part of the study in order to evaluate at least 9 subjects for MTD. Dose limiting toxicities are defined in Section [7.5.1](#), and only those DLTs that occur within the first cycle will be used for safety assessment. The BOIN design uses the following rules, optimized to minimize the probability of incorrect dose assignment, to guide dose escalation/de-escalation:

- if the observed DLT rate at the current dose is  $\leq 0.197$ , escalate the dose to the next higher dose level;
- if the observed DLT rate at the current dose is  $\geq 0.298$ , de-escalate the dose to the next lower dose level;

- otherwise, stay at the current dose.

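### From 200 mg, section 7.5.2 lists a first reduction to 150 mg while Table 4 read with Table 14 gives 100 mg, and the Table 4 increments said to support the list do not exist

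*Protocol*

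**What the plan says.** Protocol section 7.5.2 states that interruption and reduction for drug-related toxicity "will be in accordance with the Dose Modifications Instructions in" Table 4. In the column headed "Approximate Study Drug Dose Adjustment", Table 4 gives two reduction instructions: "Restart at one lower dose level" and, for a second Grade 3 occurrence, "Restart at second lower dose level". It gives no mg amount and no percentage. Tables 5, 6 and 7 (hepatic, renal, coagulation) also send subjects to one lower dose level, and the QTcF guidance in 7.5.3 refers back to Table 4.

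Section 7.5.2 then prints mg values, introduced by "The suggested dose reductions for the three lowest dose levels are as follows based on the dose reduction increments included in" Table 4. The list runs: 100 mg to 75 then 50; the step-down dose of 75 mg to 50 then 25; 200 mg to 150 then 100; 300 mg to 200 then 100. It closes by saying that final decisions on reductions come after discussion with the Sponsor's Medical Monitor.

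Dose levels are given mg values in section 14.1, Table 14, "Total Daily Dose and Respective Dose Level": level -1 (optional) is 75 mg, and levels 1 to 6 are 100, 200, 300, 400, 600 and 900 mg.

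**The concern.** The list in 7.5.2 names Table 4 as its source, and Table 4 holds nothing from which the list could be derived. Someone who follows Table 4 and looks up dose levels in the protocol's only level-to-mg table reaches a different restart dose from 200 mg than someone who follows the list.

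What is at stake is the dose given after a drug-related toxicity in a first-in-human study planned for about 20 sites, and a clean reading of later-cycle tolerability and exposure in subjects whose dose was reduced. Table 4 also governs Part 2. The SAP (section 6.2) names 100, 200 and 300 mg as the levels conducted, so the 200 mg row was in use.

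**Working it through.** There is no sample-size or error-rate calculation to reproduce. The check is a lookup: place each starting dose in the 7.5.2 list on the Table 14 ladder (75 optional, 100, 200, 300, 400, 600, 900 mg) and move down one and two levels, as Table 4 says. The second lower level is read as two levels below the starting dose.

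**With the optional 75 mg level available (first / second reduction, mg)**

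| Starting dose | Section 7.5.2 | Table 4 with Table 14 | Result |
|---|---|---|---|
| 300 | 200 / 100 | 200 / 100 | both agree |
| 200 | 150 / 100 | 100 / 75 | both differ |
| 100 | 75 / 50 | 75 / none | first agrees; second has no level |
| 75 | 50 / 25 | none / none | no level for either |

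Of the eight listed reductions, 2 + 1 = 3 agree, 2 conflict directly (both from 200 mg), and 1 + 2 = 3 point to doses that are not Table 14 levels.

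**Size of the conflict at 200 mg.** First reduction: 150/100 = 1.50, so the 7.5.2 dose is 50% higher. Second reduction: 100/75 = 1.33, so 33% higher.

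**If the optional level is not opened.** From 200 mg the ladder gives 100 mg and then nothing, so only the first reduction has a comparator. From 100 mg it gives nothing. The 75 mg row drops out as a starting dose. Of the remaining six entries, 2 agree (300 mg), 1 conflicts (first reduction from 200 mg) and 3 have no level. The 150 versus 100 mg conflict is present either way.

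**Does some unstated increment explain the list?** First steps from 75, 100, 200 and 300 mg are 75 − 50 = 25, 100 − 75 = 25, 200 − 150 = 50 and 300 − 200 = 100 mg. As a share of the starting dose they are 25/75 = 33%, 25/100 = 25%, 50/200 = 25% and 100/300 = 33%. Neither a fixed mg step nor a fixed percentage reproduces all four rows, so the missing increment cannot be recovered from the list.

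**Higher starting doses.** Section 7.5.2 gives no mg values for 400, 600 or 900 mg. There the Table 14 ladder is the only documented reading of a lower dose level, so the same phrase would be read from the ladder at those doses and from the list at 200 mg.

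**The case against.** The best defence is that the conflict is assembled from two tables that do not cite each other. Table 4 never mentions Table 14, and Table 14 sits in the statistics section as the escalation schedule. Amendment 3.0 says the 7.5.2 list was added to give more detail on modifying the dose after a treatment-related event. The list can therefore be read as the specific text that defines a lower dose level for these starting doses, and with 25 mg tablets (Table 11) every listed dose can be given. The list is suggested, the Table 4 column is approximate, and the Medical Monitor is consulted before a final decision.

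Much of this stands. The consultation means that a site should not settle a restart dose alone from whichever passage it happens to read. It does not say which passage the discussion starts from. Nor does the list present itself as a definition: it claims to derive from Table 4 increments, and there are none. Section 14.1 uses lower dose level in the ladder sense in its de-escalation rule.

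Four stronger readings are tempting, and the documents do not support them:

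- *A restart at 150 mg would be a reportable overdose.* Section 9.2 refers to an amount over the protocol-specified dose assigned to the subject. A subject assigned 150 mg from the printed list, after discussion with the Medical Monitor, is receiving the assigned dose.
- *The list covers four starting doses under a heading that promises three.* Exactly three entries are labelled as starting doses; 75 mg is labelled separately as a step-down dose.
- *Section 7.5.2 contradicts the ban on dose escalation within a subject.* It says "re-escalation can be considered in consultation" with the Medical Monitor, while section 7.1 says "No intra-patient dose escalation will be permitted". The first can be read as a return toward the assigned dose, so this is at most a point to clarify.
- *Dose-escalation conclusions are compromised.* Section 7.5.1 bars reductions in Cycle 1 of escalation, and only Cycle 1 DLTs feed the MTD rule.

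**Conclusion.** The inconsistency is real and narrow. From 200 mg, section 7.5.2 and Table 4 read with Table 14 give different doses: 150 against 100 mg for the first reduction and, if the optional level is available, 100 against 75 mg for the second. The 50 and 25 mg entries are doses without a Table 14 level rather than conflicting values, and the absence of a list above 300 mg is a gap. It would overstate the case to say that the whole list contradicts Table 4, because the 300 mg row and the first reduction from 100 mg agree with it.

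This rests on taking Table 14 as the meaning of dose level in Table 4. The protocol does not say so, but it offers no other map from level to mg. The softening language limits the practical effect without removing the conflict. DLT counts, the BOIN rules for the MTD, sample size and error rates are untouched, and the SAP plans mostly listings. It still merits correction rather than a clerical note, because it concerns the dose given after a drug-related toxicity in a first-in-human study. No view is taken on which dose is right.

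**What to change.** The sponsor should reconcile section 7.5.2, Tables 4 to 7 and Table 14:

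- Provide one table, with values set by the sponsor, giving the first and second reduction for every starting dose from 75 to 900 mg.
- Have Tables 4 to 7 refer to that table.
- Remove the mention of increments that Table 4 does not contain.
- Optionally, state whether re-escalation in 7.5.2 means only a return toward the assigned dose.

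The cost is one reference table and some cross-reference edits, with no extra data or visits. According to section 1 of the SAP, the study was terminated by May 2024, in the middle of dose escalation. The useful step now is therefore for the CSR to state which rule was applied to any subject whose dose was reduced. The protocol text should be corrected before it is reused.

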**Table 4: Dose Modifications Instructions for Grade 1 – Grade 4 study drug-related Adverse Events\***

Toxicity a	During Therapy	Approximate Study Drug Dose Adjustment b
Excluding fatigue, alopecia, nausea, vomiting, or diarrhea not receiving adequate medical treatment. For management of QTcF prolongation please refer to Section 7.5.3, AST/ALT elevations please refer to Table 5, creatinine elevations please refer to Table 6, and INR elevations please refer to Table 7.		
Grade 1		
All occurrences	Continue study drug	Maintain dose level
Grade 2c		
Toxicity	During therapy	Approximate Study Drug Dose Adjustment b
1st occurrence	Monitor as clinically indicated	Maintain dose level
2nd occurrence	Interrupt study drug until resolved to Grade $\leq 1$ or baseline b	Maintain dose level
3rd occurrence	Discontinue study drug	Restart at one lower dose level
4th occurrence		Not applicable
Grade 3c,d		
Toxicity	During therapy	Approximate Study Drug Dose Adjustment b
1st occurrence	Interrupt study drug until resolved to Grade $\leq 1$ or baseline b	Restart at one lower dose level
2nd occurrence		Restart at second lower dose level
3rd occurrence	Discontinue study drug	Not applicable
Grade 4		
Any occurrence	Discontinue study drug	Not applicable

AST = aspartate aminotransferase; ALT = alanine aminotransferase; INR = international normalized ratio

\* Subjects diagnosed with a Covid-19 positive PCR test will be discontinued from treatment.

a The term occurrences applies to same AE term and not any AE term.b An interruption of any study drug for more than 14 days due to any toxicity must be discussed with the Sponsor's or Designee Medical Monitor before treatment can be resumed.c Excluding Grade 2 and 3 anemia: Subjects are allowed to continue study drug at their current dose level with transfusion per Investigator discretion.d Use of growth factors (G-CSF, GM-CSF) is permitted as per ASCO and ESMO guidelines

### 7.5.3. Safety Management Guidelines

#### Investigation: QTcF prolongation

The QTcF is the QT interval corrected for heart rate according Fridericia's formula (QTcF). For eligibility and withdrawal, subjects QTcF value will be used. For purposes of data analysis, QTcF values will be used.

If QTcF >500 msec or QTcF prolongation >60 msec from baseline is observed at any point during the study treatment and confirmed, the below guidance must be followed:

1. Assess the quality of the ECG recording and the QT value and repeat if needed.
2. Interrupt study treatment until confirmed resolution of QTcF and as per dose reduction guidelines in [Table 4](#).
3. Determine the serum electrolyte levels (in particular hypokalemia hypomagnesemia). If abnormal, correct abnormalities before resuming study drug treatment.
4. Review concomitant medication use for other causes for QT prolongation (refer to [qtdrugs.org](http://qtdrugs.org) for known QT prolonging drugs), and for drugs with the potential to increase the risk of drug exposure related QT prolongation (e.g., concomitant use of CYP3A4 inhibitors).
5. Check study drug dosing diary and treatment compliance.
6. Increased ECG safety monitoring is recommended during or in-between subsequent visits.

**Table 5: Investigation: Hepatic**

Liver function elevation management: Elevations in AST and/ or ALT			
Grade 1	All occurrences	Continue study drug	Maintain dose level
Grade 2	1 st occurrence	Interrupt study drug until resolved to Grade $\leq 1$ or baseline	Maintain dose level
	2 nd occurrence	Interrupt study drug until resolved to Grade $\leq 1$ or baseline	Maintain dose level
	3 rd occurrence	Interrupt study drug until resolved to Grade $\leq 1$ or baseline	Restart at one lower dose level
	4 th occurrence	Discontinue study drug	Not applicable
Grade 3	1st occurrence	Interrupt study drug until resolved to Grade $\leq 1$ or baseline	Maintain dose level
	2nd occurrence	Interrupt study drug until resolved to Grade $\leq 1$ or baseline	Restart at one lower dose level
	3rd occurrence	Discontinue study drug	Not applicable
Grade 4	Any occurrence	Discontinue study drug	Not applicable

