#### **5.2.3.5. Preclinical Safety**

The nonclinical safety profile of EZM0414 was evaluated in Sprague Dawley rats and Beagle dogs. In all studies, EZM0414 was delivered by oral gavage to simulate the oral route of administration proposed for the phase 1 clinical trials. The toxicity studies included a single escalating dose study in dogs, 7-day repeat-dose toxicity studies in rats and dogs, and 28-day GLP studies with 28-day recovery phases in rats (1 study) and dogs (2 studies, initial and follow-up). GLP genetic toxicity assessments were conducted to assess the mutagenicity potential of EZM0414. In addition, a thorough investigation was conducted to evaluate the differences in toxicity observed in the 7-day (non-GLP) and 28-day (GLP) repeat-dose toxicity studies in dogs, including additional single- and repeat-dose pharmacokinetic studies in rat and dog.

Following repeat dosing of EZM0414 in rats and dogs, the primary target systems include the respiratory, immunology, coagulation, hepatic, kidney, and reproductive organs. Reduction in respiratory rate, tidal, and minute volume was seen in the 28-day GLP rat study, as well as depressed respiratory function during week 4 (males and females) and the recovery period (high dose males). Effects on lymphoid cellularity, particularly in the thymus and occasionally on germinal centers, were noted throughout the immune system in rats and dogs. Additionally, there were reproducible changes in the erythron and coagulation parameters in both species. Reproductive changes were evident in rats of both sexes in the 28-day rat study and in male dogs only in the follow-up 28-day dog study. At higher dose levels, there also was toxicity to the liver and gastrointestinal tract (rats and dogs), and the adrenal gland and skeletal muscle (rat). All

EZM0414-related effects, with the exception of reproductive effects, which minimally persisted through the recovery period, were reversible. A review of the literature suggests that the changes in the hematopoietic/immune system and the reproductive system of both sexes as well as those observed in the skeletal muscle of the rat may be the result of on-target pharmacology.

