## **7.5. Dose Adjustment Criteria**

### **7.5.1. Dose Limiting Toxicities**

Any adverse event (AE) which meets the criteria of a DLT as assessed by the Investigator and warrants action as per [Table 3](#), will be reviewed by the Safety Review Committee (SRC). No intra-patient dose reduction will be permitted in Cycle 1 of dose escalation. For subjects who require a dose interruption due to a DLT during cycle 1, the treatment will be restarted once the toxicity resolves to Grade  $\leq 1$  or baseline. However, an interruption in the administration of EJM0414, for more than 14 days will be discussed with the Sponsor's or Designee Medical

Monitor before treatment can be resumed. The DLT evaluable subjects will consist of dose escalation dose level subjects who received at least 80% of planned study treatment during cycle 1. If a subject is non evaluable, this subject will be replaced by a new subject.

Safety assessments will be performed throughout the study and at each visit. DLT period is 28 days of cycle 1 of the dose escalation part. AEs that are clearly and incontrovertibly due to the underlying disease or extraneous causes will not be considered as DLTs. All of the AEs of specified grades as listed in Table 3 will be classified as DLTs. Events will be assessed as DLTs according to the Common Terminology Criteria for Adverse Events (CTCAE 5.0), as shown in [Table 3 \(Appendix 5\)](#). When a subject is assessed to be experiencing a DLT, study treatment will be interrupted and DLTs will be managed by concomitant medication (as appropriate), treatment discontinuation, or a combination of these. All dose escalation decisions will be made by the SRC and Sponsor upon review of all available data. Determination of the MTD will be informed by all available data, including the overall tolerability of EZM0414.

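### Hy's Law is dose-limiting in Table 3, but Tables 4 and 5 have no Hy's Law rule, so a first drug-related case with AST/ALT Grade 2-3 and bilirubin Grade 2 may resume EZM0414 at the same dose

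*Protocol*

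**What the plan says.** **Definition.** Protocol Table 3 lists "Any patient meeting Hy's Law Criteria without alternate explanation" as a DLT: concurrent ALT or AST above 3xULN and total bilirubin above 2xULN, without ALP above 2xULN. The entry is separate from the criterion for non-hematologic toxicity of Grade 3 or higher.

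**Management.**
- Table 4 carves out transaminases ("AST/ALT elevations please refer to Table 5") but not bilirubin, which therefore stays under its generic rows. A first Grade 2 event there is monitored at an unchanged dose. Occurrences are counted per AE term.
- Table 5 covers "Liver function elevation management: Elevations in AST and/ or ALT". A first Grade 2 and a first Grade 3 elevation get the same instruction: hold until Grade 1 or lower, or baseline, then resume at the same dose.

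**Restart text.**
- Section 7.5.1, for a DLT interruption in Cycle 1: "the treatment will be restarted once the toxicity resolves to Grade" 1 or lower, or baseline. It also states: "No intra-patient dose reduction will be permitted in Cycle 1 of dose escalation". Discontinuation is listed as one way to manage a DLT.
- Section 7.5.2, for drug-related toxicity generally: "the treatment may restart once the toxicity has resolved to Grade" 1 or lower, or baseline, following Table 4. To continue in Cycle 2 and beyond: "Any Grade 3 or higher toxicity must have resolved to Grade 1 or baseline, unless otherwise noted".

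Outside Table 3, Hy's Law appears nowhere in the supplied protocol text or in the SAP.

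**The concern.** The protocol treats the combination of raised transaminases and raised bilirubin as important enough to limit dose, then manages each value as if the other were absent. A Hy's Law case can consist of moderate individual grades, and a grade-by-grade rule is most lenient exactly there. The subject can be re-exposed at the dose that produced the signal.

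This is a first-in-human drug. Section 5.2.3.5 reports liver toxicity at higher doses in both rats and dogs, and Section 5.3 names the hepatic system among the potential risks. Other risks have specific instructions: Section 7.5.3 gives six steps for QTcF prolongation, and Table 7 discontinues drug for any INR elevation of Grade 3 or higher. For a first Grade 3 event, Table 5 is also more lenient than the generic Table 4, which drops one dose level.

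The DLT definition applies only in Cycle 1 of escalation. From Cycle 2, and throughout Part 2, no rule looks at the two values together.

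**Working it through.** The plan gives no figure to reproduce, so the check traces the rules.

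**Assumptions.** CTCAE 5.0 cut-offs apply (Appendix 5 is not in the supplied text), baseline values are normal, the event is drug-related, and the stricter of Tables 4 and 5 governs. A Hy's Law case is then AST/ALT Grade 2, 3 or 4 with bilirubin Grade 2, 3 or 4: 3 x 3 = 9 combinations.

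**Inputs, first occurrence.**
- AST/ALT (Table 5): Grade 2 same dose; Grade 3 same dose; Grade 4 discontinue.
- Bilirubin (Table 4): Grade 2 same dose; Grade 3 one level lower; Grade 4 discontinue.

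**Result, taking the stricter action in each cell.**

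| | Bilirubin Gr 2 | Bilirubin Gr 3 | Bilirubin Gr 4 |
|---|---|---|---|
| AST/ALT Gr 2 | same dose | one lower | stop |
| AST/ALT Gr 3 | same dose | one lower | stop |
| AST/ALT Gr 4 | stop | stop | stop |

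Same dose 2, lower 2, stop 5. The two same-dose cells correspond to roughly AST/ALT >3-20xULN with bilirubin >2-3xULN.

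**Second occurrence of both values.** AST/ALT Grade 2 is still same dose, and Grade 3 goes one lower. Bilirubin Grade 2 is still same dose, and Grade 3 goes to the second lower level. Same dose 1 (Grade 2 with Grade 2), lower 3, stop 5.

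**Cycle 1 of escalation.** Reduction is barred, so the two one-lower cells become same dose if drug is restarted within the cycle: 2 + 2 = 4 of 9.

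**Sensitivity to the cut-offs.**
- If bilirubin above 2xULN were always Grade 3 or higher, 6 combinations remain: 0 same dose, 2 lower, 4 stop.
- If AST/ALT above 3xULN were always Grade 3 or higher, 6 remain: 1 same dose, 1 lower, 4 stop.

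The result therefore turns on bilirubin just above 2xULN being Grade 2. Table 3 supports that indirectly, since a separate Hy's Law entry would add little if such cases were always Grade 3 or higher.

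**Other provisions, tested on AST/ALT Grade 2-3 with bilirubin Grade 2.**
- Retreatment criteria (7.5.2): they require recovery only of Grade 3 or higher toxicity, so a Grade 2 bilirubin does not hold drug back.
- Medical Monitor: contact is required for interruptions over 14 days and for dose-reduction decisions. A shorter hold with a same-dose restart triggers neither.
- Unacceptable toxicity (7.5.4): limited to related Grade 4 or 5 events.

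**The case against.** The strongest reply is that other safeguards surround these tables.

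- **Committee review.** Section 7.5.1 sends DLTs to the Safety Review Committee, which under Section 7.5.4 includes sponsor Medical Directors and Pharmacovigilance and monitors all toxicity. This is a real mitigation, but review is not stated as a condition of restart.
- **Meaning of the toxicity that must resolve.** When the DLT is Hy's Law, Section 7.5.1 can naturally be read as requiring bilirubin to recover as well. That is fair for Cycle 1, and Section 7.5.2 uses similar words. It narrows the concern about unresolved bilirubin, but the restart is still at the same dose.
- **One diagnosis.** Section 13.2.4 prefers a clinical diagnosis to isolated test results. A case recorded as a single Grade 3 liver injury could fall under Table 4, with a one-level reduction and Medical Monitor discussion. This is a possible route, not a required one.
- **Grid.** Cells are counted equally and say nothing about frequency. For bilirubin Grade 3 in Cycle 1, holding or stopping drug is as open as restarting. Both points stand, and the figures should be read that way.
- **Context.** The animal liver effects were reversible, chemistry is checked on Days 8, 15 and 22 of Cycle 1, and the investigator may stop drug at any time. These lower the risk without supplying the rule.
- **Timing.** The SAP says the study was terminated on a business decision, and only 100, 200 and 300 mg were conducted. An amendment would change no analysis. This limits the practical value to re-use of the tables.

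**Conclusion.** The concern holds. As written, the rules permit same-dose re-exposure after a first drug-related Hy's Law event with AST/ALT Grade 2-3 and bilirubin Grade 2. Outside Cycle 1 of escalation, no explicit rule requires bilirubin to have recovered.

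The claim has limits. Grade 4 of either value means discontinuation, a first Grade 3 bilirubin drops one level outside Cycle 1 of escalation, and restart after Cycle 1 is permissive. The size rests on the CTCAE mapping and the other stated assumptions. It describes what the rules allow, not how many subjects would be affected. Because a stated rule gives a less safe result than the protocol's own DLT definition implies, this is more than missing detail. It should be corrected, but it is not critical for a study that has ended.

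**What to change.** Add one row to Table 5, applying in all cycles and both parts: if the Table 3 Hy's Law criteria are met, interrupt EZM0414 at once and discontinue permanently unless an alternate explanation is established. Add one sentence stating that this row overrides the AST/ALT-grade rows, the Table 4 handling of bilirubin and the Section 7.5.1 restart wording. Where another cause is established, the existing rows apply.

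The cost is one row and one sentence in an amendment, or in any protocol that re-uses these tables. No new tests are needed, because AST, ALT, total bilirubin and alkaline phosphatase are already in the chemistry panel.

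The downside is that a few subjects who could have tolerated rechallenge may stop drug. Subjects admitted with tumor-related AST/ALT below 5xULN may already meet the transaminase limb at entry and would depend on the alternate-explanation exception, so the investigator's reasoning should be documented for them.
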